8.3.3 EVENTS OF SPECIAL INTEREST

A graft failure will be considered an Adverse Event of Special Interest (AESI) in the MiACL trial. Graft failures will be diagnosed by the patient's physician using a combination of objective laxity (e.g. positive pivot shift) and/or MR imaging. Any such diagnosis, whether treated with an ACL reconstruction revision or not, will be characterized as an AESI. A graft failure is being considered as an AESI as the ACL graft could potentially be impacted by the interventions of interest in the study. As such, a higher than suspected number of ACL graft failures in either group could suggest the active or placebo interventions are compromising the graft tissue/ACL reconstruction and are

unsafe. It is expected that ~10% of ACL grafts will fail with autograft ACL reconstruction and standard ACL rehabilitation.

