8.3.7 ADVERSE EVENT OF SPECIAL INTEREST REPORTING

If a graft failure, the only AESI for the current study, is identified by the study team through patient reporting or review of medical records it will be monitored and reported using the guidelines discussed in section 8.3.5. If the graft failure, however, results in an ACL revision reconstruction this would result in an SAE which would be monitored and reported as discussed in section 8.3.7. Whether designated as an AE or an SAE the AESI will be flagged and specifically reported to the DSMB providing details regarding the number for each study group, and a breakdown of how the AESIs were thought to occur (traumatic or atraumatic). The AESIs will be followed for outcome information until resolution (e.g. date of revision surgery), stabilization (e.g. end of care for the AESI), or study completion, with stop dates recorded for resolution.

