9.2 SAMPLE SIZE DETERMINATION

For the main study objectives, the sample size of 112 participants (56 per each of the 2 treatment groups) allows sufficient power to test the primary hypotheses regarding two separate comparisons (each co-primary endpoint) of the combination NMES + ECC vs NMES placebo + ECC placebo. Each test will be conducted using a two-sided 0.025 Type I error level ($=0.05/2$, the Bonferroni adjustment for two comparisons). We hypothesize that the effect size (treatment difference / standard deviation) will be at least 0.7 for the tests of NMES + ECC vs NMES placebo + ECC placebo. Assuming 20% drop-out (resulting in an effective sample size of 45 per group), we have at least 80% power to detect this effect size. Preliminary data from the

same site with a comparable patient population and primary endpoint demonstrated a 1.14 effect size. Because of the small sample size and variability in measurements in this preliminary study, we conservatively reduced the effect size for this study.³⁵

An additional cohort of 28 participants will be studied – the SOC control group. The sample size of 28 participants for this group is based on feasibility considerations.

Thus, the total sample size for the trial is 140 participants.

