9.4.2 ANALYSIS OF THE PRIMARY EFFICACY ENDPOINTS

The primary hypotheses will be tested at the two-sided 0.025 level, adjusting for the multiple comparisons of 2 co-primary endpoints. Separate linear models will be fit for each of the two co-primary endpoints, one for the 9-month and one for the 18-month changes from baseline in isokinetic quadriceps muscle strength. As described above, the model will include treatment group, type of graft, surgeon, age, gender, and baseline isokinetic quadriceps strength symmetry index. Least-squares (LS) mean change from baseline, along with associated standard errors, will be presented for each intervention group. For the comparisons of combination NMES + ECC to the placebo group, group LS mean differences in the change from baseline will be presented, along with associated 97.5% upper confidence bounds and p-values. The primary analysis of the primary endpoints will use the mITT analysis set. A secondary analysis of the primary endpoints will use the PP analysis set. Appropriate non-linear parametric or non-parametric tests may be applied if the assumptions of the model are not satisfied. Details will be presented in the SAP.

Assessment of the extent of missing data and its mechanism will be explored for the primary endpoints using the mITT analysis set. Graphical and numerical descriptive methods will be used to summarize and the primary outcome over time by intervention group and overall. We will begin by assuming missing at random, and employ multiple imputation methods^{45,46} to handle missing data. Other more complicated methods may be employed if there are concerns about differential follow-up and nonignorable missing (where the stochastic process that generates missingness is explicitly modeled such as a pattern mixture model⁴⁷) as a sensitivity analysis. The model will include the same covariates that are included in the primary analysis.

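### Strength values missing because of a graft failure would be imputed under missing at random without using failure status, which can overstate the benefit if failures are more common in the active arm

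*Combined protocol and SAP*

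**What the plan says.** Graft failure is foreseen and treated as a safety event. Section 8.3.3 states: "It is expected that ~10% of ACL grafts will fail with autograft ACL reconstruction and standard ACL rehabilitation". It gives no time by which these failures occur. It makes failure an event of special interest on the ground that the study interventions might affect the graft, and adds: "Any such diagnosis, whether treated with an ACL reconstruction revision or not, will be characterized as an AESI". Section 8.3.7 covers revision conditionally ("If the graft failure, however, results in an ACL revision reconstruction this would result in an SAE") and requires reporting by study group: "Whether designated as an AE or an SAE the AESI will be flagged and specifically reported to the DSMB".

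The efficacy sections do not mention it. Section 9.3 defines the mITT set as everyone randomized who received at least one intervention, analysed as assigned. Section 7.1 keeps participants who stop the intervention in follow-up, and section 7.2 lets an investigator withdraw a participant after an adverse event. The primary model in section 9.4.2 contains treatment, graft type, surgeon, age, gender and baseline index. On missing values it says: "We will begin by assuming missing at random, and employ multiple imputation methods". Pattern-mixture or similar methods may be used if there is concern about differential or non-ignorable loss. A closing sentence says the model uses the same covariates as the primary analysis.

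**The concern.** A failed or revised graft damages the limb in the numerator of the primary index. It occurs after randomization, and the plan itself allows that treatment may influence it. If failure causes the 9- or 18-month test to be missed, the reason is known and recorded, but the stated method does not use it. Imputation from the named covariates would draw from the rest of the arm, most of whom have not failed, so the participant would be credited with something close to an ordinary recovery.

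If this happens more often in the active arm, a harm of treatment is partly removed from the efficacy estimate. The 18-month co-primary endpoint is the more exposed, since section 3 places return to activity at about 9 months and failures have longer to accumulate.

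**Working it through.** **The plan's own figure.** Section 9.2 has "112 participants (56 per each of the 2 treatment groups", 20% drop-out, and "Each test will be conducted using a two-sided 0.025 Type I error level", with an "effect size (treatment difference / standard deviation) will be at least 0.7". Then 56 × 0.80 = 44.8, rounded to 45 per arm. The noncentrality is 0.7 × √(45/2) = 3.32 on 88 df, and power is 84.9% (noncentral t). The stated minimum of 80% is reproduced, and nothing below disputes it.

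**Expected number.** 0.10 × 112 = 11.2 failures if the 10% applies by the visit analysed. If only 5% had failed by then, it would be 5.6.

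**Assumptions not in the documents.** The effect with intact grafts is 0.7 SD. A failure lowers the index by D = 1 to 2 SD, equally in both arms. A share u of failures is untested, the same in both arms. No other values are missing. Imputation without failure status reproduces the mean of the tested participants in the same arm.

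**Formulas.** Let pA and pP be the failure rates in the active and placebo arms.
- Difference with every participant's actual value: T = 0.7 − (pA − pP) × D.
- Share of failures among those tested in an arm: q = p(1 − u)/(1 − pu).
- Difference after imputation: E = 0.7 − (qA − qP) × D.
- Overstatement: E/T − 1.

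**Worked case, 15% versus 5%, u = 0.5.** qA = 0.075/0.925 = 0.0811 and qP = 0.025/0.975 = 0.0256, a difference of 0.0554. For D = 1, T = 0.60, E = 0.645, overstatement 7.4%. For D = 2, T = 0.50, E = 0.589, overstatement 17.8%.

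**Range (D = 1 to D = 2).**

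| Failures, active vs placebo | 20% untested | 50% untested | All untested |
|---|---|---|---|
| 15% vs 5% | 2.8 to 6.7% | 7.4 to 17.8% | 16.7 to 40.0% |
| 15% vs 10% | 1.2 to 2.6% | 3.3 to 7.2% | 7.7 to 16.7% |
| 12.5% vs 7.5% | 1.3 to 2.8% | 3.4 to 7.4% | 7.7 to 16.7% |
| 10% vs 10% | 0 | 0 | 0 |

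The direction reverses if the active arm has fewer failures. At 5% versus 10%, D = 1 and all untested, T = 0.75 and E = 0.70, an understatement of 6.7%.

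**What the zero row rests on.** It requires a failure to cost the same in both arms. If failed knees instead lose the whole treatment benefit, equal 10% rates give T = 0.9 × 0.7 = 0.63. With all failures untested E = 0.70, an overstatement of 0.70/0.63 − 1 = 11%. With half untested E = 0.7 × (1 − 0.05/0.95) = 0.663, an overstatement of 5%.

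**The case against.** Much can be said for the plan. mITT by assigned treatment and continued follow-up already imply that a value measured after failure is used as observed, so tested participants have a default. Section 7.1 seeks 18-month strength and MRI data in participants who do not complete the interventions, and nothing suggests that all failures go untested. Failures are reported to the DSMB by group, so the harm is not concealed from safety oversight. Section 9.4.2 promises to explore the missingness mechanism and names pattern-mixture models. The separate SAP that section 9.4 calls for is not among the documents reviewed and could contain a rule. All of this stands, and it limits the size of the problem. It does not put failure status into the imputation or make the sensitivity analysis compulsory, and graft failure is not among the topics that the protocol assigns to the SAP.

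Three stronger readings are tempting but not supported.
- A reader might infer that failures are imputed as if the graft were intact. The imputation model is not fully specified, the closing covariate sentence may describe only the sensitivity model, and the draws would include any failures that were tested. *Mainly from participants without failure* is as far as the text goes.
- A reader might infer that the trial is underpowered because of failures. Section 9.2 does not say that 0.7 is an intact-graft effect, some failures may already sit within the 20% drop-out, and a rule for missing values would not change any loss that comes from values used as measured.
- A reader might take 40% as the expected bias. It needs every failure untested, a threefold imbalance between arms and a 2 SD loss. It also puts the placebo arm at half the rate that section 8.3.3 gives for standard rehabilitation.

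**Conclusion.** The point holds as a weakness in the stated missing-data rule. The plan anticipates a fairly common event that treatment may influence and records it for every participant, but does not name it as an input when imputing the values that it causes to be missing. The 18-month estimate can be biased, in favour of the active arm if that arm has more failures.

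Under the illustrative 15% versus 5% split, the overstatement is 3 to 7% with a fifth of failures untested, 7 to 18% with half, and 17 to 40% with all. With equal rates, equal missingness and equal cost of failure there is none. The failure split, the 1 to 2 SD loss and the untested share are all assumptions, because the documents give no strength data after failure. The 10% is undated, so the effect at 9 months is probably smaller. It is worth correcting before database lock, but it does not invalidate the design.

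**What to change.** In section 9.4.2, or in the SAP before lock and unblinding:

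(a) Confirm that values measured after graft failure or revision are used as observed under mITT.

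(b) Include graft failure before the visit as a predictor in the multiple imputation, with one coefficient pooled across arms because numbers are small. The special-interest flag (section 8.3.7) and the onset date (section 8.3.6) are already collected.

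(c) Make the pattern-mixture analysis mandatory for values missing after graft failure, shifting the imputed values downward by a prespecified range of amounts. This is preferable to fixing them at zero change from baseline: that baseline is a pre-operative injured knee, so zero change has no support in the documents and may not be conservative.

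Section 9.4.3 specifies no imputation for the T1rho and T2 ratios. If they are imputed, use the same flag.

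The cost is SAP wording and a little more analysis. The imputation will be less stable if few failures are tested: with 11 failures and half tested, only 5 or 6 inform the coefficient, and with none tested it cannot be estimated, so (c) has to carry the weight. The estimate may also turn out less favourable.

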1.2 SCHEMA – TREATMENT GROUPS

1.3 SCHEMA – SOC CONTROL GROUP

1.4 SCHEDULE OF ACTIVITIES (SOA)

Procedures	Pre-Screening (Phone and Record Review)	Testing Visit 1 Enrollment/BaseLine	Repeat Testing Visit 1 ^d	ACL Surgery	Intervention or SOC PT Visits 1-16 ^f	Testing Visit 2 Post-NMES Intervention	Intervention or SOC PT Visits 17-32 ^g	Testing Visit 3 Post-ECC Intervention	Testing Visit 4 9 months post-ACLR ^c	12 months post-ACLR	15 months post-ACLR	Testing Visit 5 18 months post-ACLR ^c
Days on Study (relative to ACLR)	-365	-30	-30	0	1-70	N/a ^h	56-126	N/a ^h	270	365	455	540
Visit Window (days)- Treatment Group	0	0	0	0	0	+7	0	+7	±30	±14	±14	±30
Informed consent/assent	X											
Inclusion/Exclusion	X	X	X	X								
ACL Reconstruction Surgery					X							
Demographics		X										
Medical history		X	X									
Clinical Knee X-ray Record Review		X										
Pregnancy test ^a		X	X									
Randomization ^b					X							
Concomitant medication review	X											X
Administer NMES or placebo ^e					X							
Administer ECC or placebo ^e							X					
Standard of Care Rehabilitation monitoring					X			X				
Height & Weight	X	X							X			X
Assessment of Adverse Events	X											X
Knee X-ray		X	X									X
Knee MRI												X
Quadriceps/Knee Ultrasound		X	X			X		X	X			X
Thigh Muscle Strength Assessment		X	X			X		X	X			X
Quadriceps Activation Assessment		X	X			X		X	X			X
Physical Activity Monitoring										X	X	
Questionnaires		X	X			X		X	X			X
Gait Biomechanics		X	X						X			X
Clinical Hop Testing									X			X
Hopping Biomechanics									X			X
Optional Muscle Biopsy		X	X					X				X

^a Urine pregnancy test for women of child bearing potential

^b Randomization will occur after ACL reconstruction and implemented at first intervention visit. SOC control group will not be randomized.

^c Testing procedures will be scheduled within a 30 day window before or after 9 and 18 month testing date

^d Completed if Testing Visit 1 falls out of window

^e Does not apply to SOC control group

^f Intervention or SOC PT visits 1-16 can take place beginning on post-op day 1 but may begin up to 2 weeks after surgery.

^g Intervention or SOC PT visits 17-32 can take place beginning on day of Testing Visit 2 but may begin up to 2 weeks following that visit.

^h Testing Visit 2 and 3 will take place within 7 days of the last intervention or SOC PT visit.

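### Section 9.4.2 does not bring post-baseline strength into the imputation; if its only covariate rule governs the imputation model, imputing a missing outcome adds nothing to complete cases

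*Combined protocol and SAP*

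**What the plan says.** All references are to the protocol.

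- Section 9.4.2, analysis: "Separate linear models will be fit for each of the two co-primary endpoints", one for 9 months and one for 18 months. For each, "the model will include treatment group, type of graft, surgeon, age, gender, and baseline isokinetic quadriceps strength symmetry index". None of these terms is measured after baseline except the assigned arm.
- Section 9.4.2, missing data: the plan starts from MAR and uses multiple imputation. It then allows more complex methods, such as a pattern-mixture model, as a sensitivity analysis if differential or non-ignorable loss is a concern. The paragraph closes with "The model will include the same covariates that are included in the primary analysis".
- Section 1.4 lists "Thigh Muscle Strength Assessment" at baseline and at Testing Visits 2, 3, 4 (9 months) and 5 (18 months). Section 8.1 describes thigh strength on a Cybex dynamometer at each of these visits.
- Sections 4.1 and 9.4.9 give Visit 2 and 3 strength one use: an exploratory look at the separate components of the intervention.
- Section 9.2 plans for loss: "Assuming 20% drop-out (resulting in an effective sample size of 45 per group), we have at least 80% power to detect this effect size".
- Section 9.4 defers detail to an SAP that is to be final before database lock and unblinding. The text available contains no imputation specification beyond section 9.4.2.

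**The concern.** Imputation helps with a missing outcome only if the imputation model knows something that the analysis model does not. If both hold the same covariates and only the outcome is missing, the imputed values are drawn from the regression already fitted to the completers. The treatment estimate is then the complete-case estimate plus simulation noise.

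Two things would be lost. The smaller is precision. The larger is the credibility of MAR, which would have to hold given arm and baseline factors alone. A participant's strength after the intervention, or at 9 months, is an obvious candidate for predicting both the 18-month result and the decision to return. Section 7.2 allows withdrawal for non-compliance, adverse events or inability to tolerate the intervention dosage, and the arms differ in intensity, so loss that differs by arm is plausible. If weak responders leave one arm more than the other, the complete-case contrast is biased, and imputation from the same covariates carries that bias through unchanged.

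**Working it through.** **Inputs from the protocol.** Section 9.2: "the sample size of 112 participants (56 per each of the 2 treatment groups"), "We hypothesize that the effect size (treatment difference / standard deviation) will be at least 0.7", 20% drop-out, and "Each test will be conducted using a two-sided 0.025 Type I error level". Covariates are from section 9.4.2.

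**Assumed inputs.** The partial correlation r between interim strength and the endpoint, given the covariates, is not in the documents; 0.3 to 0.9 is used. The drop-out mechanisms are also assumed.

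**1. The plan's own figure.** 56 × 0.8 = 44.8, rounded to 45 per arm. Normal approximation: power = Φ(0.7 × √(45/2) − 2.241) = Φ(3.320 − 2.241) = Φ(1.079) = 86.0%. With the noncentral t it is 84.9%. Both meet the stated floor of 80%, and the calculation already assumes that only 45 per arm are analysed.

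**2. Same-covariate imputation against complete cases.** Simulation: 112 participants, true effect 0.70 in units of the residual SD, one baseline covariate, 20% lost at random, 50 imputations, 1,500 runs. At r = 0.5, complete cases gave a mean estimate of 0.693, empirical SD 0.210 and mean SE 0.212. Imputation from the analysis covariates gave 0.693, 0.210 and 0.213. Nothing is gained.

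**3. Precision from adding interim strength.** With 20% of outcomes missing and the interim value seen in every drop-out, the variance of an arm mean is (1 − r²)/44.8 + r²/56 in units of the residual variance. Effective n is its inverse.

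- r = 0.3: 0.91/44.8 + 0.09/56 = 0.02192, so n = 45.6
- r = 0.5: 0.75/44.8 + 0.25/56 = 0.02121, so n = 47.2
- r = 0.7: 0.51/44.8 + 0.49/56 = 0.02013, so n = 49.7
- r = 0.9: 0.19/44.8 + 0.81/56 = 0.01871, so n = 53.5

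Normal-approximation power is 86.5%, 87.7%, 89.4% and 91.6%, against 85.8% at 44.8 per arm. At r = 0.5 to 0.7 the variance falls by 1 − 44.8/47.2 = 5% to 1 − 44.8/49.7 = 10%. If only half of the drop-outs have the interim value, 56 becomes 50.4 in the second term, and effective n at r = 0.5 and 0.7 is 46.1 and 47.4.

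**4. Bias when drop-out depends on interim strength.** Illustrative worst case: about 19% lost, weaker participants leaving the active arm and stronger ones leaving the placebo arm; true effect 0.70.

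| r | Complete cases | Imputation, analysis covariates | Imputation with interim strength |
|---|---|---|---|
| 0.3 | 0.806 | 0.806 | 0.705 |
| 0.5 | 0.874 | 0.873 | 0.706 |
| 0.7 | 0.946 | 0.946 | 0.713 |
| 0.85 | 0.985 | 0.985 | 0.700 |

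The complete-case bias is 0.11, 0.17, 0.25 and 0.29 SD. The Monte Carlo error of each mean is about 0.21/√1500 = 0.005. The mechanism is symmetric, so each arm contributes half. With informative loss in one arm and random loss in the other, the bias for r = 0.3 to 0.7 would be 0.106/2 = 0.05 to 0.246/2 = 0.12 SD. A separate simulation of that one-arm case (3,000 trials per scenario, 9-to-18-month correlation 0.6 to 0.8) gave 0.10 to 0.12 SD, and 0.19 to 0.23 SD for opposite directions.

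**The case against.** The sentence says what the model will include and sets no limit. The analysis covariates belong in any sound imputation model, and no section excludes further variables. The sentence also follows directly on the pattern-mixture option and may describe only that. A reader might infer that the plan rules out interim strength; the documents do not support so strong a reading. What stands is that, whichever model is meant, nothing in the protocol uses post-baseline strength for a missing primary outcome.

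Section 9.4 promises a detailed SAP, and section 9.4.2 undertakes to examine the missingness mechanism and allows other methods if follow-up differs by arm. This is a partial answer. Those methods are optional, and an SAP author who applied the one stated rule to the imputation model would get complete-case results.

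A reader might also infer that the primary endpoint itself is recorded at Visits 2 and 3. The documents establish thigh strength on the dynamometer at those visits, but not explicitly the isokinetic symmetry index; section 4.1 places the primary outcomes at baseline, 9 and 18 months. Nor does 9-month strength help with a missing 9-month value, since it is that value. There the candidates are Visits 2 and 3 and, where obtained, 18 months. Section 7.1 does commit to seeking 18-month strength after treatment is stopped.

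Finally, the near-zero bias with interim strength is partly by construction: the simulated drop-out depends on the very variable supplied to the imputation. Some drop-outs will lack interim data, since section 7.3 defines loss to follow-up by four missed visits. That limits the gain but does not remove it.

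**Conclusion.** The point holds conditionally. If the rule in section 9.4.2 governs the imputation model, imputing a missing primary outcome gives the complete-case answer, and MAR rests on arm and baseline covariates alone. This assumes that only the outcome is missing; imputing missing covariates could recover a little.

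The main reason to act is validity. The possible bias is roughly 0.1 SD with informative loss in one arm. In the opposite-direction worst case it is about 0.1 to 0.25 SD for assumed correlations of 0.3 to 0.7, and slightly more at 0.85. Against the 0.7 design effect, 0.1 and 0.25 are 14% and 36%. The sign depends on who leaves which arm. None of these correlations or mechanisms comes from the documents, so the figures show what could happen and do not forecast what will.

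A reader might infer that the trial is underpowered as a result. It is not: the sample size already discounts the 20% lost, and at least 80% power is reproduced.

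**What to change.** State which model the closing sentence of section 9.4.2 refers to, and keep it for the sensitivity model if that is its meaning. Then specify the imputation model in section 9.4.2 or the SAP before unblinding, for example:

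*The imputation model will include treatment arm, all covariates of the primary analysis, the quadriceps strength measures recorded at Testing Visits 2 and 3, and the isokinetic symmetry index at baseline, 9 months and 18 months, with the 9- and 18-month values imputed jointly. Imputation will be done by arm or with arm interactions; sparse surgeon levels will be pooled where needed. The analysis model is unchanged.*

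The SAP should name the exact strength variable available at Visits 2 and 3.

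The cost is SAP wording and a few lines of code, using strength data already scheduled for collection. The downside is a somewhat larger imputation model: with 56 per arm and surgeon and graft terms, imputing by arm can produce sparse cells, hence the pooling. The benefit shrinks where drop-outs also lack interim data.
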